10.2. Populations for Analysis

Populations for analysis are shown in **Table 16**.

Table 16: Populations for Analysis

Population	Description
Efficacy evaluable	
The efficacy evaluable population includes all enrolled participants who received at least 1 dose of study drug.
 
The efficacy evaluable population will be used for the summary of demographics, baseline characteristics, participant disposition, and analyses of all efficacy data.

Safety	The safety population includes all enrolled participants who received at least 1 dose of study drug. All safety analyses will be conducted using the safety population.
Per protocol	The per protocol population includes all efficacy evaluable population participants who are sufficiently compliant with the protocol.

10.3. Level of Significance

The overall level of significance is 1-sided 0.05.

10.4. Statistical Analyses

10.4.1. Primary Analysis

The primary endpoint of the study is ORR. Objective response rate is defined as the proportion of participants who achieved a CR or a PR based on RECIST v1.1 or RANO, as assessed by local radiological review. This analysis will be based on the efficacy evaluation population. Participants who do not have sufficient baseline or on-study response assessment information to be adequately assessed for response status will be included in the denominators in the calculation of ORR. The 90% CI for the ORR will be estimated using the Clopper-Pearson method. The p-value from the exact binomial test will be provided.

The ORR will also be analyzed based on the per protocol population as a sensitivity analysis.

10.4.2. Secondary Efficacy Analysis

Secondary efficacy analysis will be conducted for the efficacy evaluable population.

Progression-free survival is defined as the time from date of first dose of study drug to the date of progressive disease or death, whichever is first. Progressive disease is evaluated based RECIST v1.1, or RANO, by the local radiographic review. Participants who are alive without progression before analysis cutoff date will be censored. Censoring for PFS will follow FDA guidance. Progression-free survival data will be analyzed by the Kaplan-Meier method.

For objective responders, DOR is defined as the time from the date a participant first achieves CR or PR based on RECIST v1.1 or RANO until the date of first documented disease progression based on RECIST v1.1 or RANO or death. Participants who are alive without progression before analysis cutoff date will be censored. Censoring of DOR will follow the same algorithm as the censoring of PFS. Duration of response data will be analyzed by the Kaplan-Meier method.

Disease control rate, defined as the proportion of participants who achieved best overall response of CR, PR, or SD per RECIST v1.1 or RANO, and its exact 90% CI will be calculated in each cohort.

Overall survival is defined as the time from date of first dose of study drug to death due to any cause. Participants without death observed at the time of the analysis will be censored at last date known to be alive. Overall survival will be analyzed by the Kaplan-Meier method.

10.4.3. Safety Analyses

Safety analyses will be conducted for the safety population. Adverse events will be coded by the MedDRA dictionary, and TEAEs (ie, AEs reported for the first time or worsening of a pre-existing event after first dose of study drug/treatment) will be tabulated by preferred term and system organ class for all events, related events, and events of Grade 3 or higher.

Quantitative safety variables and their changes from baseline (eg, laboratory, vital signs) will be summarized with descriptive statistics. Clinically notable abnormal values will be flagged and tabulated based on predefined criteria.

The clinical laboratory data will be analyzed using summary statistics; no formal treatment group comparisons are planned. In addition, distributions of key laboratory parameters may be plotted over time; these values will also be classified into CTCAE toxicity grades, and tabulated.

Descriptive statistics and mean change from baseline will be determined for vital signs at each assessment time. Vital sign results will be reviewed for clinically notable abnormalities.

Descriptive statistics and mean change from baseline will be determined for each ECG parameter at each assessment time. Electrocardiogram results will be reviewed for clinically notable abnormalities according to predefined criteria (see Section 8.3.4). Participants exhibiting clinically notable ECG abnormalities will be listed.

Measures of exposure of study drug will be summarized by means of summary statistics.

10.5. Interim Analysis

No formal interim analysis is planned. However, each tumor subtype within each cohort will be assessed when 10 or more participants are enrolled.

11. SUPPORTING DOCUMENTATION AND OPERATIONAL CONSIDERATIONS

11.1. Investigator Responsibilities

- The Protocol, Protocol amendments, ICF, IB, and other relevant documents (eg, advertisements) must be submitted to an IRB/IEC by the investigator and reviewed and approved by the IRB/IEC before the study is initiated.
- The investigator is responsible for ensuring that the safety reports provided by the sponsor are reviewed and processed in accordance with regulatory requirements, the policies and procedures established by the IRB/IEC, and institutional requirements.
- Any amendments to the Protocol will require IRB/IEC approval before implementation of changes made to the study design, except for changes necessary to eliminate an immediate hazard to study participants.
- The investigator will be responsible for the following:
 - Providing written summaries of the status of the study to the IRB/IEC annually or more frequently in accordance with the requirements, policies, and procedures established by the IRB/IEC.
 - Notifying the IRB/IEC of SAEs or other significant safety findings as required by IRB/IEC procedures.
 - Providing oversight of the conduct of the study at the site and adherence to GCP, IRB/IEC requirements, institutional requirements, and applicable laws and country-specific regulations.
- Adhering to the Protocol as described in this document and agreeing that changes to the Protocol procedures, with the exception of medical emergencies, must be discussed and approved, first, by the sponsor or its designee and, second, by the IRB/IEC. Each investigator is responsible for enrolling participants who have met the specified eligibility criteria.
- Retaining records in accordance with all local, national, and regulatory laws, but for a minimum period of at least 2 years after the last marketing application approval in an ICH region and until there are no pending or contemplated marketing applications in an ICH region, or if not approved, 2 years after the termination of the test article for investigation to ensure the availability of study documentation should it become necessary for the sponsor or a regulatory authority to review.
 - The investigator must not destroy any records associated with the study without receiving approval from the sponsor. The investigator must notify the sponsor or its designee in the event of accidental loss or destruction of any study records. If the investigator leaves the institution where the study was conducted, the sponsor or its designee must be contacted to arrange alternative record storage options.
 - All eCRF data entered by the site (including audit trail), as well as computer hardware and software (for accessing the data), will be maintained or made available at the site in compliance with applicable record retention regulations. The sponsor will retain the original eCRF data and audit trail.

11.2. Data Management

Data management will be performed in a validated EDC system. The investigator will be provided with access to an EDC system so that an eCRF can be completed for each participant.

The site will be provided eCRF completion guidelines for instructions on data entry in the eCRF. The study monitor will reference the Monitoring Plan in order to ensure that each issue identified is appropriately documented, reported, and resolved in a timely manner in accordance with the plan's requirements. Other data outside the EDC system required in the study conduct of the protocol such as documents or results transmitted to the sponsor via a central laboratory or specialized technical vendors, and as designated by the sponsor, will have their own data flow management plans, or study charters, [REDACTED], as applicable.

The sponsor (or designee) will be responsible for:

- Managing the integrity of the data and the quality of the conduct of the study, such as ensuring that study monitors perform ongoing source data verification to confirm that data entered into the eCRF by authorized site personnel are accurate, complete, and verifiable from source documents; that the safety and rights of participants are being protected; and that the study is being conducted in accordance with the currently approved protocol and any other study agreements, ICH GCP, and all applicable regulatory requirements.
- Managing and reconciling the data generated, and/or collected including documents and results such as laboratory or imaging data analyzed centrally by a designated vendor of the sponsor.

The investigator will be responsible for:

- Recording, or ensuring the recording of, all relevant data relating to the study in the eCRF.
- Delivering, or ensuring the delivery of, all other results, documents, data, know-how, or formulas relating to the study to the sponsor or designee electronically and/or centrally (e.g., laboratory data, imaging data, [REDACTED] photographs, diary data), or as otherwise specified in the Protocol.
- Verifying that data entries are accurate and correct by physically or electronically signing the eCRF.
- Maintaining accurate documentation (source data) that supports the information entered in the eCRF, or sent to a central vendor designated by the sponsor, or as described in other study and data flow manuals.
 - Source documents provide evidence for the existence of the participant and substantiate the integrity of the data collected. Source documents are filed at the investigator's site.
 - Data entered in the eCRF that are transcribed from source documents must be consistent with the source documents or the discrepancies must be explained. The investigator may need to request previous medical records or transfer records, depending on the study. Also, current applicable medical records must be available.

- May have responsibility for sending participants' data, either as unique samples, or copies, or photographs, to be evaluated centrally or analyzed centrally, or both, by a qualified vendor designated by the sponsor.
- Permitting study-related monitoring, sponsor audits, IRB/IEC review, and regulatory inspections by providing direct access to source data and other relevant clinical study documents.
 - Monitoring: Qualified representatives of the sponsor or its designee, study monitors, will monitor the study according to a predetermined plan. The investigator must allow the study monitors to review any study materials and participant records at each monitoring visit.
 - Auditing: Qualified representatives of the sponsor or its designee may audit the clinical study site and study data to evaluate compliance with the Protocol, applicable local clinical study regulations, and overall study conduct. The investigator must allow the auditors to review original source records and study documentation for all participants.
 - Regulatory inspection: Regulatory authorities may conduct an inspection of the study and the site at any time during the development of an investigational product. The investigator and staff are expected to cooperate with the inspectors and allow access to all source documents supporting the eCRFs and other study related documents. The investigator must immediately notify the sponsor when contacted by any regulatory authority for the purposes of conducting an inspection.

11.3. Data Privacy and Confidentiality of Study Records

The investigator and the sponsor or its designee must adhere to applicable data privacy laws and regulations. The investigator and the sponsor or its designee are responsible for ensuring that sensitive personal information is handled in accordance with local data protection laws (including but not limited to HIPAA and GDPR) as applicable. Appropriate consent for collection, use and disclosure and/or transfer (if applicable) of personal information must be obtained in accordance with local data protection laws.

Participant names will not be supplied to the sponsor or its designee. Only the participant number will be recorded in the eCRF; if the participant's name appears on any other document (eg, laboratory report), it must be obliterated on the copy of the document to be supplied to the sponsor or its designee. Study findings stored on a computer will be stored in accordance with local data protection laws.

Records and documents, including signed ICFs, pertaining to the conduct of this study must be retained by the investigator for 5 years after study completion unless local regulations or institutional policies require a longer retention period. No records may be destroyed during the retention period without the written approval of the sponsor. No records may be transferred to another location or party without written notification to the sponsor.

11.4. Financial Disclosure

Before study initiation, all clinical investigators participating in clinical studies subject to FDA Regulation Title 21 CFR Part 54 – Financial Disclosure by Clinical Investigators (ie, "covered studies") are required to submit a completed Clinical Investigator Financial Disclosure form that sufficiently details any financial interests and arrangements that apply. For the purpose of this regulation, "clinical investigator" is defined as any investigator or subinvestigator who is directly involved in the treatment or evaluation of research participants, including the spouse and each dependent child of the clinical investigator or subinvestigator. These requirements apply to both US and foreign clinical investigators conducting covered clinical studies.

Any new clinical investigators added to the covered clinical study during its conduct must also submit a completed Investigator Financial Disclosure Form. During a covered clinical study, any changes to the financial information previously reported by a clinical investigator must be reported to the sponsor or its designee. At the conclusion of the covered clinical study, the clinical investigators will be reminded of their obligations. In the event that the clinical investigator is not reminded, they nevertheless will remain obligated to report to the sponsor or its designee any changes to the financial information previously reported, as well as any changes in their financial information for a period of 1 year after completion of the covered clinical study.

11.5. Publication Policy

By signing the study Protocol, the investigator and his/her institution agree that the results of the study may be used by the sponsor, Incyte Corporation (Incyte), for the purposes of national and international registration, publication, and information for medical and pharmaceutical professionals. Study results will be published in accordance with applicable local and national regulations. If necessary, the authorities will be notified of the investigator's name, address, qualifications, and extent of involvement. The terms regarding the publication of study results are contained in the agreement signed with the sponsor or its designee. A signed agreement will be retained by the sponsor or its designee.

The results of this study may be published or presented at scientific meetings. If this is foreseen, the investigator agrees to submit all manuscripts or abstracts to the sponsor before submission. This allows the sponsor to protect proprietary information and to provide comments.

The sponsor will comply with the requirements for publication of study results. In accordance with standard editorial and ethical practice, the sponsor will generally support publication of multicenter studies only in their entirety and not as individual site data. In this case, a coordinating investigator will be designated by mutual agreement.

Authorship will be determined in line with International Committee of Medical Journal Editors authorship requirements.

11.6. Study and Site Closure

The sponsor designee reserves the right to close the study site or terminate the study at any time for any reason at the sole discretion of the sponsor. Study sites will be closed upon study completion. A study site is considered closed when all required documents and study supplies have been collected and a study-site closure visit has been performed.

The investigator may initiate study-site closure at any time, provided there is reasonable cause and sufficient notice is given in advance of the intended termination.

Reasons for the early closure of a study site by the sponsor or investigator may include but are not limited to:

- Failure of the investigator to comply with the protocol, the requirements of the IRB/IEC or local health authorities, the sponsor's procedures, or GCP guidelines.
- Inadequate recruitment of participants by the investigator.
- Discontinuation of further study treatment development.

APPENDIX A. INFORMATION REGARDING EFFECTIVENESS OF CONTRACEPTIVE METHODS

For male participants in the study:

Male participants should use a condom from screening through 90 days after the end of systemic exposure. If the male participant has a partner that is of child-bearing potential, the partner should also use contraception through 90 days after the end of relevant systemic exposure. In addition, male participants must refrain from donating sperm from screening through 90 days after the end of relevant systemic exposure. Males who have had a vasectomy qualify as having met the requirement for a highly effective birth control method.

For female participants in the study:

The following methods that can achieve a failure rate of less than 1% per year when used consistently and correctly are considered as highly effective birth control methods:

- Combined (estrogen and progestogen containing) hormonal contraception associated with inhibition of ovulation^a
 - oral
 - intravaginal
 - transdermal
- Progestogen-only hormonal contraception associated with inhibition of ovulation^a
 - oral
 - injectable
 - implantable^b
- Intrauterine device^b
- Intrauterine hormone-releasing system^b
- Bilateral tubal occlusion^b
- Vasectomized partner^{b,c}
- Sexual abstinence^d

Acceptable birth control methods that result in a failure rate of more than 1% per year include:

- Progestogen-only oral hormonal contraception, where inhibition of ovulation is not the primary mode of action
- Male or female condom with or without spermicide^e
- Cap, diaphragm, or sponge with spermicide^e
- Tubal ligation

^a Hormonal contraception may be susceptible to interaction with the investigational medicinal product, which may reduce the efficacy of the contraception method.

^b Contraception methods that in the context of this guidance are considered to have low user dependency.

^c Vasectomized partner is a highly effective method of avoiding pregnancy provided that partner is the sole sexual partner of the woman of childbearing potential study participant and that the vasectomized partner has received medical assessment of the surgical success.

^d In the context of this guidance, sexual abstinence is considered a highly effective method only if defined as refraining from heterosexual intercourse during the entire period of risk associated with the study treatments. The reliability of sexual abstinence needs to be evaluated in relation to the duration of the clinical study and the preferred and usual lifestyle of the participant.

^e A combination of male condom with either cap, diaphragm, or sponge with spermicide (double barrier methods) are also considered acceptable, but not highly effective, birth control methods.

Source: [Clinical Trial Facilitation Group 2014](#).

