5.1. Inclusion Criteria

Participants are eligible to be included in the study only if all of the following criteria apply:

1. Ability of the participant (or parent, guardian, or legally authorized representative) to comprehend and willingness to sign the ICF.
2. Age 18 years or older, inclusive at the time of signing the informed consent.
3. Histologically or cytologically confirmed solid tumor malignancy that is advanced or metastatic (Stage IIIB or IV per the [American Joint Committee on Cancer, Cancer Staging Manual, 6th Edition](#)) or is surgically unresectable.
4. Radiographically measurable disease (per RECIST v1.1 or RANO for primary brain tumors). Tumor lesions located in a previously irradiated area or in an area subjected to other loco-regional therapy are considered measureable if progression has been clearly demonstrated in the lesion.
5. Documentation of an FGFR1-3 gene mutation or translocation (see Section [8.4](#) and [Appendix C](#)).
6. Objective disease progression after at least 1 prior therapy, and there is no further approved therapy available that is likely to provide clinical benefit. Participants who are intolerant to or decline the approved therapy are eligible only if they have no therapy available that is likely to provide clinical benefit.
7. ECOG performance status 0 to 2.

8. Baseline archival tumor specimen (if less than 12 months from date of screening) available or willingness to undergo a pretreatment tumor biopsy to obtain the specimen. Must be a tumor block or approximately 15 unstained slides from biopsy or resection of primary tumor or metastasis.
9. Not eligible or able to participate in any other Incyte Sponsored Clinical Trial.
10. Willingness to avoid pregnancy or fathering children based on the criteria below.
 - a. Men must agree to take appropriate precautions to avoid fathering children (with at least 99% certainty) from screening through 90 days after the last dose of study drug and must refrain from donating sperm during this period. Permitted methods that are at least 99% effective in preventing pregnancy (see [Appendix A](#)) should be communicated to the participants and their understanding confirmed.

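### For men, the contraception instruction in Appendix A can be followed without reaching the 99% level that inclusion criterion 10a sets

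*Protocol*

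**What the plan says.** Protocol Section 5.1, criterion 10a, sets the standard for men: "Men must agree to take appropriate precautions to avoid fathering children (with at least 99% certainty". It then refers to Appendix A for the methods that qualify: "Permitted methods that are at least 99% effective in preventing pregnancy". Sites must explain these methods and confirm that the participant understands them.

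The male paragraph of Appendix A gives three instructions that matter here:

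- For the man: "Male participants should use a condom from screening through 90 days after the end of systemic exposure".
- For the woman: "If the male participant has a partner that is of child-bearing potential, the partner should also use contraception", for the same 90-day period.
- On vasectomy: "Males who have had a vasectomy qualify as having met the requirement for a highly effective birth control method".

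The section for female participants then gives two lists. The first holds methods with a failure rate below 1% per year, which the appendix calls highly effective. The second holds methods with a failure rate above 1% per year. Condoms are on the second list, and so are caps, diaphragms and sponges with spermicide. Footnote e covers the two barriers together: "A combination of male condom with either cap, diaphragm, or sponge with spermicide (double barrier methods) are also considered acceptable, but not highly effective".

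The first list includes "Bilateral tubal occlusion" and the second includes "Tubal ligation".

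**The concern.** An eligibility criterion and the appendix it cites should lead a site to the same answer. Here the criterion sets a numerical level, while the male paragraph names one method that falls short of it when used alone and leaves the partner's method open. A site that counsels a couple from the male paragraph alone could accept a combination that the appendix itself classes below the required level.

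What is at stake is prevention of fetal exposure through male participants. Section 9.6 requires pregnancies under maternal or paternal exposure to be reported, but that comes after the event. The scheduled pregnancy tests are for female participants and do not cover a man's partner. Section 5 allows no deviation from eligibility criteria, so a misreading cannot be put right by a waiver.

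**Working it through.** No formula from the statistical section applies, and the plan gives no figure to reproduce. The check compares texts, with one conversion and a count.

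**Threshold.** Criterion 10a asks for 99%. The complement is 100% − 99% = 1% failure. Appendix A draws its line at 1% per year. Criterion 10a gives no time unit, so equating the two is an assumption; it uses the appendix's own line.

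**Count from Appendix A.**

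- Methods the male paragraph names as highly effective: 1 (vasectomy).
- Effectiveness levels it states for the partner: 0.
- Female section: 7 methods below 1% per year and 4 entries above 1% per year.

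**Couples tested against both texts** (partner of childbearing potential throughout):

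| Couple | Follows the male paragraph on method? | Meets the 10a level? |
|---|---|---|
| Vasectomized man | Vasectomy expressly credited | Yes |
| Condom, partner on one of the 7 methods below 1% | Yes | Yes |
| Condom, partner using cap, diaphragm or sponge with spermicide | Yes | No: footnote e places the pair below highly effective |
| Condom, partner on another entry of the list above 1% | Yes | Appendix gives no class for the combination; no claim made |

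The third row is the documented conflict. It concerns 1 of the 4 second-list entries, which covers three devices. The couple uses a condom and the partner uses contraception, so both sentences are obeyed. Footnote e then puts exactly that pair outside the class that 10a needs.

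**Tubal entries.** Criterion 10c accepts hysterectomy, bilateral oophorectomy or at least 12 months of amenorrhea as nonchildbearing status. A woman with a tubal procedure who meets none of these stays under 10b. Criterion 10b asks her to agree to adequate precautions, and any method from the first list satisfies it. If tubal ligation is in the wrong list, the effect is to ask for more contraception, not less.

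**The case against.** The strongest reply is that there is no real conflict. Criterion 10a is the binding rule and already filters for methods that are at least 99% effective; Appendix A only supplies information on effectiveness. Footnote e tells a careful reader that the double-barrier pair does not qualify. The vasectomy sentence presupposes that men face a highly effective requirement, and the definition and list follow directly below it. Since the partner is a woman of childbearing potential, that list is the natural reference, and 10a also requires sites to confirm understanding.

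Much of this stands. A site that reads 10a, the male paragraph, the female list and footnote e together would exclude the pair. A reader might infer that the protocol lets men enroll below 99%; it does not, because 10a is not displaced.

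The reply does not clear the male paragraph itself. The list of methods below 1% sits under the heading for female participants, and the male text neither refers to it nor limits the partner to it. Its only named route to the required level is vasectomy. The sensible reading has to be assembled by the site.

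Two further inferences are tempting but unsupported:

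- **Tubal ligation makes a woman eligible at one site and ineligible at another.** Criterion 10b is not a test of one past procedure, and she can add a first-list method. Nor do the documents say that the two tubal terms mean the same thing: only one is qualified as bilateral, and only that one carries the footnote on low user dependency.
- **The second list's description as acceptable authorizes those methods for women.** The same heading states a failure rate above 1% per year and 10b states 99%, so relabelling it would only repeat what is there.

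**Conclusion.** The point holds as a conflicting instruction for non-vasectomized men with a partner of childbearing potential. Following the male paragraph of Appendix A does not guarantee meeting criterion 10a, and one combination that follows it is expressly classed too low.

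The size is limited. Vasectomized men and men whose partner uses a method from the first list are unaffected. How many of the approximately 50 participants could be affected cannot be derived from the protocol and may be zero. Response rate, sample size and analysis do not change.

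The conclusion assumes that 99% effectiveness corresponds to at most 1% failure per year. It makes no claim about combinations that the appendix leaves unclassified. The tubal entries are a minor query only: any error there is conservative and does not by itself exclude a woman. The point is still worth correcting, because it concerns a safety rule at enrollment and the correction is small.

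**What to change.** In the male section of Appendix A, replace the open-ended partner sentence with a requirement along these lines: unless the man is vasectomized, he must use a condom, and a partner of childbearing potential must use a method from the highly effective list (failure below 1% per year), for the period already stated.

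Separately, ask the sponsor to confirm that tubal ligation and bilateral tubal occlusion are meant to be in different classes and to say how they differ, or else to reconcile the two entries. The other entries of the second list need no change.

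The cost is a line or two in Appendix A. The consent pages are not available here; if they repeat this text, they need the same wording. Design, sample size and analysis stay as they are.
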